5.4.2 Sample Size Considerations

We calculated the sample size based on the primary cognitive outcome, i.e., Neuro-QoL version 2 Cognitive Function scores. The Neuro-QoL Cognitive Function validation study with 120 PD patients who had mild disease (Hoehn & Yahr stage 2) showed mean \pm SD = 50.46 \pm

7.25.⁹⁷ A change of 2-6 T-scores have been considered a minimally important change in patient-reported outcome measures.¹⁰³

We estimated the sample size based on the assumption that there will be an average of 4 T-score improvement after mental imagery training using the G*Power 3.1 software^{104,105}. The repeated-measures ANOVA between-subject factor model with two groups and two measurements, with an effect size of $f=0.266$ (corresponding to a moderate effect size $d=0.53$), alpha 0.05, and power 0.80 yielded a total sample size of 86 (43 in each group). With an estimated 15% drop out ($86/0.85 \approx 101$) during the 6-week intervention period and another 15% drop out ($101/0.85 \approx 120$) in the subsequent 12-week period, we plan to recruit 120 subjects in total.

In our previous work with PD patients using motor (N=22) and visual (N=22) imagery training, we showed robust task-specific pairwise functional connectivity changes post-training especially in the respective motor and visual networks.⁴ Therefore, we think this sample size will also be adequate for the primary imaging outcome.

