4.2 Outcome Variables

4.2.1 Primary Outcome Variables

1) Quality of life in Neurological Disorders (Neuro-QoL) Scores

Timeframe: This measure will be collected at baseline (T0), immediately after 6 weeks of intervention (T1), and 12 weeks thereafter (T2) from all subjects.

Rationale: The Neuro-QoL is a set of self-report measures that assesses the health-related quality of life of adults and children with neurological disorders. Neuro-QoL instruments were developed through a collaborative, multisite NINDS-sponsored research initiative to construct psychometrically-sound and clinically-relevant health-related quality of life measurement tools for individuals with neurological conditions including PD. The Neuro-QoL instruments enable within-disease as well as cross-disease comparisons and are intended for use in both neurology clinical trials and clinical practice. We will use the Neuro-QoL version 2 Cognitive Function item bank to assess post-training self-reported changes in cognitive functions.

Change in the Neuro-QoL version 2 Cognitive Function scores from T0 to T1 and across T2 will be the primary cognitive outcomes of this study. Significant increase in the Cognitive Function scores at T1 will be considered significant improvement in self-reported cognitive function in everyday life. Significant increase in these scores across T2 will be considered sustained improvement in self-reported cognitive function in everyday life.

2) Questionnaire on Mental Imagery (QMI) Vividness of Imagery Scale scores

Time frame: This measure will be collected at baseline (T0), immediately after 6 weeks of intervention (T1), and 12 weeks thereafter (T2) from all subjects.

Rationale: The QMI is a measure of vividness of an individual's multisensory and motor imagery on a scale of 1 to 7 (1: perfectly vivid image, 7: no image present at all).

Change in the QMI scores from T0 to T1 and across T2 will serve as the manipulation check for the mental imagery intervention. Significant increase in these scores at T1 will be considered improved imagery vividness. Significant increase in these scores across T2 will be considered sustained improvement in imagery vividness.

3) Task-specific whole-brain pairwise functional connectivity

Time frame: This measure will be collected at baseline (T0), immediately after 6 weeks of intervention (T1), and 12 weeks thereafter (T2) from all subjects.

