5.4 Statistical Method

5.4.1 Statistical Design

This is a phase 1 randomized clinical trial aiming to enroll 120 subjects with Parkinson's disease (PD) assigned in parallel to the experimental PD-MI (N=60) and active control PD-Con (N=60) groups. The units of observation are the subjects in these groups. Subjects will be enrolled continuously and randomized to two groups using the "minimization" method.¹⁰¹ After truly randomly allocating the first 10 subjects, each subsequent subject will be allocated to either group considering the factors age, gender, and disease stage. This method will allow us to minimize the imbalance between the groups in terms of demographic and clinical characteristics while at the same time preserving the randomness of group allocation.

We will use independent-sample t-tests and nonparametric Mann-Whitney U tests to compare subjects characteristics between the PD-MI and PD-Con groups.

We will use mixed ANOVA tests with interaction terms to assess the short- and longer-term changes in cognitive and imaging outcomes before and after training.

Our overall statistical approach is designed to address the outcomes of four different aims:

AIM 1: To determine the effects of mental imagery training on goal-directed everyday cognitive functioning in PD

Primary outcome: Change in Neuro-QoL version 2 Cognitive Function scores.⁹⁷

Manipulation check: Change in QMI Vividness of Imagery Scale scores.¹⁰⁰

Neuro-QoL version 2 Cognitive Function scores (Visit 1) and QMI scores (Visit 2) obtained at baseline and immediately upon conclusion of the 6-week intervention (Visit 3) will be compared between the PD-MI and PD-Con groups using a 2x2 mixed ANOVA with an interaction term (dependent variables: test scores, between-subject factor: group, within-subject factor: time with two levels, i.e., baseline and post-training, interaction: group-by-time) ($p < 0.05$, two-tailed).

Secondary outcomes: Change in composite z-scores obtained from the executive function tests.

We will calculate a composite z-score from the executive function test scores (i.e., Stroop,⁹⁴ F-A-S letter fluency,⁹⁵ and Trail Making A-B tests⁹⁶) for all subjects.

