The primary, secondary and exploratory outcomes as outlined in Aims 1 and 2 will also apply to Aim 3. All cognitive and functional MRI tasks will be repeated 12 weeks after the completion of the training program (Visit 4). These results will then be compared with those obtained at baseline and 6-week post-intervention using a 3x2 mixed ANOVA with an interaction term (dependent variables: cognitive test scores and functional connectivity and graph measures, between-subject factor: group, within-subject factor: time with three levels, i.e., baseline, 6-weeks post-intervention, and 12-weeks post-completion, interaction: group-by-time) ($p < 0.05$, two-tailed). A significant interaction will be followed by post hoc simple effects tests to determine the level(s) of interaction.

AIM 4: To explore the brain-cognition link associated with mental imagery training in PD

Exploratory Aim: We will examine the post-training brain-cognition relationship at the 6-week and 12-week timepoints in each group. We will test whether the post-training changes in task-specific whole-brain pairwise functional connectivity and graph measurements will predict the post-training differences in the Neuro-QoL Cognitive Function and composite executive test scores in each group.

Exploratory outcomes: This brain-behavior relationship at 6 weeks will be the exploratory outcome of Aim 2 and that at 12 weeks will be the exploratory outcome of Aim 3.

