5.4.6 Handling of Missing Data

We assume that the missing data will be missing at random. If the proportion of missing data is not more than 5%, we will ignore the missing data and perform complete case analyses. Otherwise, we will use multiple imputation to replace the missing data at follow-up for the primary cognitive outcome. Regardless of the proportion of missing data, we will constrain the voxelwise imaging analyses to complete cases because to our knowledge, there is no validated method to correct for missing data in such analyses.

6 Trial Administration

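### The 80% power at N=86 is for the group main effect averaged over baseline and follow-up, not for the T1 group-by-time interaction, and it depends on a visit correlation the plan does not state

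*Combined protocol and SAP*

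**What the plan says.** Section 5.4.2 bases the size on the primary cognitive outcome: "We calculated the sample size based on the primary cognitive outcome, i.e., Neuro-QoL version 2 Cognitive Function scores". It quotes a validation-study SD of 7.25 and assumes "there will be an average of 4 T-score improvement after mental imagery training". The G*Power model is "The repeated-measures ANOVA between-subject factor model with two groups and two measurements", with f=0.266 (given as d=0.53), alpha 0.05 and power 0.80, which yields 86 in total (43 per arm). Two successive 15% losses, the first "during the 6-week intervention period and another 15% drop out" over the next 12 weeks, raise this to 120. No correlation between visits is given there or anywhere else in the protocol.

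Section 4.2.1 defines the outcome as change: "Change in the Neuro-QoL version 2 Cognitive Function scores from T0 to T1 and across T2 will be the primary cognitive outcomes". For Aim 1, section 5.4.1 compares the arms with a 2x2 mixed ANOVA with group as the between-subject factor and "within-subject factor: time with two levels, i.e., baseline and post-training, interaction: group-by-time", two-tailed at 0.05. For Aim 3 the three visits are compared "using a 3x2 mixed ANOVA with an interaction term". Section 5.4.6 adds that if more than 5% of data are missing, "we will use multiple imputation to replace the missing data at follow-up for the primary cognitive outcome".

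**The concern.** The between-subject factor in a repeated-measures ANOVA compares the arms on each patient's mean over the visits. In a randomised trial the arms are expected to be equal at baseline, so a training benefit appears as a difference in change, which is the interaction. The plan appears to report power for one term and to rely on the other.

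The distinction matters because the two terms respond to the between-visit correlation in opposite ways. A high correlation makes the average over visits noisier and the change less noisy. Without that correlation a reader cannot convert the stated 80% into power for the planned comparison. Two other inputs are also unexplained: the SD behind d=0.53, and the control-arm change assumed when an improvement after imagery training is used as a difference between arms.

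**Working it through.** **Inputs.** From 5.4.2: f=0.266, d=0.53, a 4-point effect, SD 7.25, alpha 0.05, 1:1 allocation, N=86, 15% loss in each period, N=120 recruited. From 5.4.1: two-tailed test, 2x2 and 3x2 mixed ANOVA. The correlation rho is not in the documents, so 0.3 to 0.7 is shown as an assumption. Unless stated otherwise, the control arm is assumed not to change.

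**1. The plan's own figure.** For the between-subject factor with m=2 visits, the noncentrality is lambda = N·f²·m/(1+(m−1)·rho), with 1 and N−2 df. At rho=0.5, N=84 gives power 0.794 and N=86 gives 0.804. So 86 is reproduced, but only for rho of about 0.48 to 0.51; 0.47 gives 84 and 0.52 gives 88.

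**2. The SD.** 4/7.25 = 0.552, whereas d=0.53 implies 4/0.53 = 7.55. The stated d is the more conservative value. Both are carried below.

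**3. The planned T1 comparison.** With two visits the interaction is a two-sample test of change scores. The SD of change is SD·√(2(1−rho)), so the standardised effect is d/√(2(1−rho)). In interaction form, lambda = N·f²·m/(1−rho) with f = d/4 = 0.1325 for a difference present only after training. Total N for 80% power at d=0.53:

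| rho | Sized model (main effect) | Planned interaction |
|---|---|---|
| 0.3 | 76 | 160 |
| 0.4 | 80 | 138 |
| 0.5 | 86 | 114 |
| 0.6 | 92 | 92 |
| 0.7 | 98 | 70 |

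At the plan's N=86 and rho=0.5, the interaction has 68% power (d=0.53) or 72% (d=0.552).

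**4. Power with the recruited number.** Completers at T1: 120 × 0.85 = 102, or 51 per arm. If imputation lost no information, all 60 per arm would count, which is an upper bound. Values are for d=0.53 / d=0.552.

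| rho | 51 per arm | 60 per arm (upper bound) |
|---|---|---|
| 0.3 | 61.0 / 64.5% | 68.2 / 71.7% |
| 0.4 | 67.7 / 71.2% | 74.8 / 78.1% |
| 0.5 | 75.5 / 78.8% | 82.1 / 85.0% |
| 0.6 | 84.2 / 87.0% | 89.6 / 91.8% |
| 0.7 | 92.8 / 94.5% | 96.1 / 97.2% |

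With 51 per arm, 80% is passed at rho of about 0.55 (d=0.53) or 0.52 (d=0.552). Simulation with 20,000 runs at rho=0.5 gave 75.8% and 79.1%.

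**5. Control-arm change (illustration).** If controls gained 1 point and the imagery arm 4, the difference is 3 points. With SD 7.25, rho=0.5 and 51 per arm, power falls from 79% to 54%.

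**6. How far apart the two tests are.** If the 4-point difference exists only after training, the averaged difference is 2 points. The sized test then has 29 / 31% power at N=86 and rho=0.5. This shows the mismatch; it is not the trial's power.

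**7. T2.** Completers: 120 × 0.85² / 2 ≈ 43 per arm. For the 3x2 interaction under compound symmetry, lambda = 2n·Σ((δt − mean δ)/2)²/(1−rho), where n is the number per arm and δt the standardised difference at visit t, with 2 and 2(2n−2) df. At rho=0.5, power is 71 / 75% if the effect is fully sustained and 58 / 62% if half fades by T2. At rho=0.6 it is 81 / 84% and 68 / 72%.

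**The case against.** The strongest reply is that nothing here shows harm to the trial. At the correlation that reproduces the plan's own N, T1 power with the expected completers is 75.5–78.8%, and with a somewhat higher correlation it exceeds 80%. A baseline-adjusted analysis of the T1 score reaches 80% with 43 per arm (rho=0.5, d=0.53). In a phase 1 study meant to inform later trials, this is an error in one paragraph. That stands, and it limits the severity. It does not make the stated figure correct.

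A second reply is that Aim 1 lists group, time and their interaction without saying which term decides, and that section 4.2.1 speaks only of a significant increase in scores at T1. Taking the interaction as the deciding term is therefore a reading, but it is the only one that fits an outcome defined as change compared between arms. The group term does not measure change, and the time term does not compare arms.

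A third reply is that the calculation itself is sound. It is: the fault lies in the choice of model and the missing correlation. It is also fair to say that section 5.4.2 makes no separate power claim for T2, and that the fading and compound-symmetry assumptions are not in the documents, so those figures are illustrative.

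**Conclusion.** The concern holds and should be fixed. The 80% in section 5.4.2 belongs to the group main effect at an unstated correlation of about 0.5, not to the comparison of change at T1. With 51 completers per arm, that comparison has 61–65% power at rho=0.3, 76–79% at 0.5 and 93–95% at 0.7. At rho=0.5 the shortfall from 80% is 1.2 to 4.5 points.

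These figures assume a full between-arm difference of 4 points (or d=0.53), equal SDs at both visits and no control-arm gain; any gain in controls lowers them. Whether the trial falls short of 80% cannot be settled from the documents, because they do not give rho. The correlation range is an assumption, but the mismatch between the sized test and the planned test does not depend on it.

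**What to change.** Rewrite the power paragraph of section 5.4.2 for the T1 group-by-time interaction, and state:

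1. the assumed between-arm difference in T0–T1 change;
2. the SD used and the resulting d (0.53 implies about 7.5; 7.25 gives 0.55);
3. the between-visit correlation and its source;
4. the assumed control-arm change;
5. the analysis basis, about 51 completers per arm, noting that section 5.4.6 plans multiple imputation above 5% missing.

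Then report power at 51 per arm for rho from 0.3 to 0.7. Do not re-enter f=0.266 in the within-between interaction option: at rho=0.5 it returns N=30, because f there is a different quantity. For a difference present only after training at d=0.53, f is 0.1325 (N=114 at rho=0.5). If T2 power is reported, compute it for the 3x2 interaction under a stated time profile.

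Optionally, analyse the T1 score adjusted for baseline and change section 5.4.1 to match. The standardised effect becomes d/√(1−rho²), giving 86% power at 51 per arm (rho=0.5, d=0.53). The correction does not require this.

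The cost is one rewritten paragraph, plus a sentence in 5.4.1 if the optional analysis is chosen. N=120 stays, with no extra patients or visits. The stated power may look slightly less favourable.

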5.4.3 Planned Analyses

Analysis of executive function and performance-based tests

We will obtain a composite executive function score by averaging the z-transformed individual scores on the Stroop, letter fluency (F-A-S), and Trail Making A-B tests.⁹⁴⁻⁹⁶ A total score will be calculated for the RBANS. We will calculate the Modified Six-Element Test score as the number of subtasks attempted minus the number of violations of the task switching rules.⁹⁸

Analysis of behavioral data during scanning

We will adopt the qualitative analysis approach used in our previous study.⁴ We will add up the number of key elements of the recorded mental imagery descriptions for each scan (e.g., entities, sensory descriptions, spatial/temporal references, thoughts, actions, emotions, task components) and average them across scans to obtain an average imagery content score per subject. We will also average the number of correct answers to content-related questions after video-watching scans to obtain an average accuracy score per subject. These scores will then be used in statistical analyses.

Preprocessing of fMRI data

We will use the CONN toolbox for all fMRI data analysis steps.⁵³ Removal of the first four scans to reach magnetization steady state, motion correction, outlier detection, coregistration of functional scans with the anatomical scan, normalization to the standard MNI template, and smoothing with an 8-mm kernel to account for inter-individual anatomical variability will be performed. De-noising steps will include the elimination of signal originating from the white matter and cerebrospinal fluid, regression of motion artifacts and outliers from the time series, linear detrending, and high-pass filtering ($0.008 < f < \text{Inf}$).

Pairwise functional connectivity analysis

To compare the task-specific whole-brain functional connectivity changes between the groups, we will perform pairwise functional connectivity analyses using the generalized psychophysiological interaction (gPPI) model. We will first convolve the 3-min task blocks in each mental imagery and video-watching run with the canonical hemodynamic response function. We will use the functionally defined cortical and subcortical nodes (N=268) of the whole-brain Shen atlas.⁵² For each subject, we will extract the average blood oxygenation level-dependent signal time courses calculated via the gPPI model from these nodes and correlate them with each other using Pearson correlations. The r values will correspond to the functional connectivity strength between node pairs. We will Fisher z-transform the r values and obtain group-level functional connectivity maps for statistical analyses.

Graph analysis

To compare the task-specific changes in local and global network properties between the groups, we will perform graph analyses on the pairwise functional connectivity data. Specifically, we will compute the 1) clustering coefficient, which shows the connectivity strength between neighboring nodes and is a measure of local network efficiency, and 2) betweenness centrality, which shows how well-connected a particular node is with all other nodes and is a measure of that node's potential as an integrative hub.¹⁰⁶ These graph measures will then be used in statistical analyses.

Sex as a biological variable

Sex differences in normal cognitive aging have been reported.¹⁰⁷ Reports on sex differences in PD-related cognitive decline have been variable. Sex differences in cognition in de novo PD patients have been found to be similar to those in normal aging.¹⁰⁸ On the other hand, male sex was found to be associated with PD-MCI,¹⁰⁹ and poorer performance in male vs female PD patients in executive functioning and processing speed have been demonstrated.¹¹⁰ In our study, both groups will be sex-matched and we will use sex as a covariate in separate analytical models to examine the potential sex-related differences in training response.

5.4.4 Analysis of Subject Characteristics

We will perform independent-sample t-tests to compare the normally distributed continuous baseline data (e.g., MoCA, MDS-UPDRS) and nonparametric Mann-Whitney U tests to compare the discrete baseline data (e.g., symptom onset side, Hoehn & Yahr score) and non-normally distributed continuous data between the PD-MI and PD-Con groups ($p < 0.05$, two-tailed) using the statistical software package SPSS (IBM SPSS Statistics version 28). If the nonmotor survey data (e.g., mood, fatigue) differ significantly between the groups, we will use them as covariates in the mixed ANOVA tests explained above.

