5.1.1 Data Collection

The data will be collected specifically for this project. The information obtained in this study will be recorded in such a manner that the identity of the human subjects cannot be ascertained directly. The data will not contain personally identifiable information and will be labeled using a coding system. The data labels will contain the subject code, date and time of recording, and mode and condition of recording. Only the principal investigator, [name], will have access to the centrally and electronically stored and password-protected subject identification list to decode data files. All other study investigators will have access to the de-identified data. All study investigators will use encrypted research computers.

Data Recording

Case report forms for each subject will be used to enter clinical evaluation results, and scores of paper-pencil tests, surveys, and performance-based tests. All of this information will

then be entered into a password-protected electronic database, which will be stored in a group-owned ([name] Lab) shared space on a Yale REDCap database. This is a secure web application for building and managing online surveys and databases. It is specifically geared to support online or offline data capture for research studies and operations.

Imaging data obtained at the MRRC will be transferred securely to workstations for analysis and stored on HIPAA-compliant secure central storage servers ("Storage@Yale") provided by the Yale IT Department for a monthly fee. All team members will use encrypted research computers.

Sources of Data

Initial Screening: Data will be collected at meetings with the subjects via phone call and Zoom video platform.

- Demographic data (age, sex, ethnicity, level of education, etc.)
- MRRC MRI safety questionnaire
- Medical history questionnaire
- MoCA test for global cognition
- PD Cognitive Functional Rating Scale for daily functional abilities

Online Surveys: These surveys will be administered via the Yale REDCap online survey platform to those who pass the initial screening. The selected surveys aim to evaluate the contribution of nonmotor factors (e.g., mood disorders, fatigue) to cognitive functioning. The survey data will be exported from REDCap.

- Geriatric Depression Scale
- Parkinson Anxiety Scale
- Starkstein Apathy scale
- PD Quality of Life Questionnaire-39
- Parkinson Fatigue Scale
- Scales for Outcomes in Parkinson's Disease – Sleep

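### Covariates could be fixed in advance at almost no cost, and sex entered as a plain covariate does not measure a sex difference in training effect (minor, ancillary)

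*Combined protocol and SAP*

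**What the plan says.** Section 5.4.1 describes minimisation: after the first ten subjects, "each subsequent subject will be allocated to either group considering the factors age, gender, and disease stage". The cognitive outcomes at six weeks are then tested with "between-subject factor: group, within-subject factor: time with two levels, i.e., baseline and post-training, interaction: group-by-time", and Aim 3 extends this to "between-subject factor: group, within-subject factor: time with three levels, i.e., baseline, 6-weeks post-intervention, and 12-weeks post-completion, interaction: group-by-time". No covariate appears in either model. Age and disease stage are not named as covariates anywhere in the document.

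Nonmotor scores enter conditionally, under section 5.4.4: "If the nonmotor survey data (e.g., mood, fatigue) differ significantly between the groups, we will use them as covariates in the mixed ANOVA tests". Six surveys are collected, and section 5.1.1 gives the reason: "The selected surveys aim to evaluate the contribution of nonmotor factors (e.g., mood disorders, fatigue) to cognitive functioning". It does not say that any of them predicts change over six weeks.

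Sex has its own paragraph in section 5.4.3: "we will use sex as a covariate in separate analytical models to examine the potential sex-related differences in training response". No sex-by-group or sex-by-group-by-time term is named there or elsewhere.

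**The concern.** There are three separate questions.

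(a) If allocation is balanced on factors that predict the outcome and the analysis ignores them, the standard error does not credit the balance. The test becomes somewhat conservative and forgoes power.

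(b) Under random allocation a significant baseline difference is a chance event. It says nothing about whether the score predicts change. With six surveys tested at 0.05, at least one would trigger by chance in 1 − 0.95^6 = 26.5% of trials if they were independent (24%, 21% and 16% at assumed pairwise correlations of 0.3, 0.5 and 0.7). The final model is therefore not known in advance.

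(c) A sex difference in training effect is a difference between arms. A sex covariate is pooled over arms. A significant sex term could be reported as men and women responding differently to imagery training when the benefit over psychoeducation is the same in both.

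**Working it through.** **Scale.** Section 5.4.2 gives SD 7.25, f = 0.266 (d = 0.53), a 4 T improvement and N = 86. It gives no pre-post correlation ρ. For the between-factor repeated-measures F with two measurements, λ = N·f²·2/(1+ρ). The smallest even N with power of at least 0.80 is 86 only for ρ of about 0.48 to 0.515; at ρ = 0.5, power is 0.804 at 86 and 0.794 at 84. So the stated figure is reproduced.

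With two time points the group-by-time test is a t-test on change, with SD of change = SD·√(2(1−ρ)). Three values are defensible:
- 7.25·√(2 × 0.5) = 7.25 T, from the cited SD.
- 4/0.532 = 7.52 T, the SD implied by the stated effect size (d = 2f = 0.532) at 4 T, again with ρ = 0.5.
- 6.54 T, the value at which 4 T has 80% power with 43 per arm.

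Unadjusted power for 4 T at 43 per arm is 0.80, 0.715 and 0.68 at SD 6.54, 7.25 and 7.52.

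**(a) Allocation factors.** A stable effect of age, sex or stage on level cancels in the change score, so only their R² with change matters. The documents do not give it; 0 to 0.20 is assumed. Simulation: 15,000 trials per cell, 120 allocated, first ten at random, then minimisation on age tertile, sex (59% men) and stage, with random loss to 86. The coin bias (0.7 to 1.0) and stage split are assumed and varied; SD 7.25 was run at one setting.

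| R² | SD 6.54: power unadjusted / adjusted | Size, unadjusted | SD 7.25: power unadjusted / adjusted |
|---|---|---|---|
| 0 | 0.79–0.80 / 0.79–0.80 | 0.049–0.051 | 0.72 / 0.71 |
| 0.05 | 0.80–0.81 / 0.81 | 0.044–0.050 | 0.72 / 0.73 |
| 0.10 | 0.81 / 0.83–0.84 | 0.041–0.044 | 0.71 / 0.75 |
| 0.20 | 0.81–0.82 / 0.87–0.88 | 0.035–0.039 | 0.72 / 0.80 |

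At R² = 0 adjusting loses about 0.5 to 0.8 percentage points. The covariate must be crossed with time: in 200 simulated data sets, a covariate entered as a main effect only left the two-time group-by-time F unchanged.

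**(b) Significance trigger.** 20,000 trials, 43 per arm, SD 6.54, one score with an assumed correlation with change.

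| Correlation | Unadjusted | Trigger | Always adjusted | Share of gain captured |
|---|---|---|---|---|
| 0.2 | 0.796 | 0.797 | 0.810 | 0.001/0.014 |
| 0.3 | 0.804 | 0.807 | 0.833 | 0.003/0.029 |
| 0.5 | 0.804 | 0.812 | 0.895 | 0.008/0.091 |

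At 0.1 or below there is nothing to gain. Size under the trigger was 0.044 to 0.054, against 0.049 to 0.054 unadjusted. A rerun at SD 7.25 and 7.52 lowered all three powers together and left the captured share at about a tenth or less.

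**(c) Sex.** Table 2 sums to 71 men and 49 women, which scales to about 51 and 35 among 86 completers. On change scores:
- Covariate model (group + sex): SE of the sex term = SD·√(1/51 + 1/35), or 1.44, 1.59 and 1.65 T at SD 6.54, 7.25 and 7.52.
- Interaction model (adding sex × group): SE = SD·√(4/51 + 4/35), or 2.87, 3.18 and 3.30 T.

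Same training effect in both sexes, with a sex difference in change common to both arms (assumed). The sex covariate is significant in:

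| Common difference | SD 6.54 | SD 7.25 | SD 7.52 |
|---|---|---|---|
| 1 T | 11% | 10% | 9% |
| 2 T | 28% | 24% | 22% |
| 4 T | 78% | 70% | 67% |

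In the simulated 4 T case (SD 6.54 and 7.25) the interaction was significant in 5%.

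For a true differential D with control men and women changing equally, the covariate averages 0 and D and so estimates D/2: 2.0 T when D = 4 T. If the arms' sex differences are −D/2 and +D/2, it averages to zero. At D = 8.2 T the covariate then rejects in 4%, the interaction in 81% (72% at SD 7.25).

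The interaction is imprecise: its 95% CI half-width is 5.7, 6.3 and 6.6 T at the three SDs. At SD 6.54 and 7.25, power for a 4 T differential is 28% and 24%, and 80% power needs 8.1 and 9.0 T. That is beyond the range in section 5.4.2: "A change of 2-6 T-scores have been considered a minimally important change in patient-reported outcome measures".

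**The case against.** For (a) and (b) the strongest reply is that nothing is wrong. The unadjusted group-by-time test is valid, the trigger rule is written down beforehand, and any gain rests on a relation with change that the documents do not supply. This stands. These are improvements, and not quite free, since a useless covariate costs a fraction of a power point.

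For (c), the sentence lists no model terms. The separate models might include the interaction. The protocol also uses training for both arms' programmes (section 5.2), so training response could mean change under one's own programme. Separate could also mean fitted by group, as Aim 4 does. This stands as ambiguity. But section 5.4.1 writes the interaction out for each group comparison it plans, and the sex paragraph writes none. By-group models would give a sex difference in each arm without comparing the two.

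The 78% deserves caution. It assumes a common sex difference as large as the whole 4 T training effect assumed in section 5.4.2, which no passage supports. At 1 T the figure is about 10%, only modestly above the nominal 5%. And for a 4 T differential confined to the imagery arm, the two tests reject about equally often (27% against 28% at SD 6.54), although the covariate estimates half the size.

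**Conclusion.** (a) and (b) are inexpensive improvements. (c) is wrong as written on its plain reading, but it is one sentence about an ancillary analysis; the point is minor.

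A reader might infer three stronger things, none of which the documents support:
- That leaving out the allocation factors invalidates or underpowers the primary test. It does not: size stays at or below nominal within simulation error, and the lower power at SD 7.25 or 7.52 comes from the SD, not from missing covariates.
- That the significance trigger inflates type I error. In simulation it does not.
- That the sex wording endangers the trial's main conclusion. The sex models are separate from the primary group-by-time test, which does not change.

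The sizes rest on assumed values for R² with change, survey correlations, the minimisation settings, the common sex difference, and a change SD between 6.54 and 7.52 T. The direction of each conclusion does not depend on which SD is used. That a pooled sex term is not a sex difference in training effect follows from the model itself.

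**What to change.** Section 5.4.1: for the cognitive outcomes, pre-specify age, sex and Hoehn & Yahr stage as covariates with their time interactions, or as covariates in the equivalent change-score model.

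Section 5.4.4: drop the significance trigger. Name the nonmotor covariates in advance on prognostic grounds, or use none.

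Section 5.4.3: name a sex-by-group-by-time term and report it as an exploratory estimate with its confidence interval (half-width about 6 T), not as a confirmatory test. If the separate models already contain this term, say so.

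Cost: wording only. All variables are already collected and no patients are added. Each of age, sex and stage (as a score) uses one degree of freedom, plus one per named survey. If the three allocation factors turn out not to predict change, the loss is under one power point.
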